## 11.0 (925) Study/Project Synopsis

11.1 \* Click on the bar below and provide a synopsis of the research study addressing the following FOUR  
 ( items USING these numbered subheadings. **Please be sure to provide enough detail that the IRB  
 ) **understands clearly what you propose to do, with whom, and why.****

- 1      1. Purpose/Objectives of the Study
- (      2. Study Population (including any inclusion/exclusion criteria)
- )      3. Study Procedures, and
- :      4. Planned Analyses

### 1. PROJECT OBJECTIVES

#### Background and Specific Aims

Dietary assessment is used to determine the nutrient intake of individuals and groups. Accurate dietary assessment is essential to nutrition research to understand how diet impacts health. Currently, there is no gold standard or single method of dietary assessment that is applicable for all nutrition research questions, as the purpose, population of interest, and resources available in any investigation impact the method of assessment that can be implemented. The current dietary assessment methods have limitations that can affect accuracy of dietary data. Currently, subjective dietary assessment methods are widely used in research. However, these subjective methods are prone to errors due to issues of accuracy of capturing all foods and beverages consumed as a consequence of recall errors and determining portion sizes of foods and beverages consumed due to poor estimation or inaccurate measurements. Self-reported dietary data also appears to have a systematic bias, in which populations with obesity are more likely to underreport intake. Subjective methods are also labor-intensive in regards to data collection and/or analysis. Objective dietary assessment can limit human errors and provide objective dietary information. However, few objective methods are available in free-living situations, and objective methods can be costly and difficult to use in studies with large samples. The incorporation of technology into dietary assessment, such as image-assisted dietary assessment, has been investigated by researchers to improve accuracy in collecting dietary information in free-living situations. The active dietary assessment methods, which is self-administered and requires individuals to manually capture images or videos with digital cameras, smartphones, and other devices with picture-capturing function, had improved accuracy and provided comparable accuracy of dietary information when compared with objective dietary

assessment methods. However, the active dietary assessment methods still rely on humans to manually capture images, which does not eliminate human errors. Passive dietary assessment methods, which images or videos automatically capture dietary intake through the use of wearable devices or other tools, can reduce human errors as the process of collecting dietary information by reducing the effort and training needed to obtain imagery. The results of reviewed passive dietary assessment methods showed improved accuracy in assessing dietary information. However, all the image-assisted dietary assessment methodologies at this time involve manual image analysis processes, which increases cost. Thus, there is a need for a wearable device that has the function of passive image capturing, with complete automated image analysis software to provide accurate and inexpensive dietary information.

Therefore, the purpose of this investigation is to validate a passive image-assisted dietary assessment method using images taken by Sony Smarteyeglass and an automatic image analysis software, DietCam, to identify food items and estimate portion sizes. The specific aims of this investigation are: 1) to determine the accuracy of DietCam in identifying foods in different shapes (Regular vs Irregular) and complexities (Single food vs Mixed food); and 2) to determine the accuracy of DietCam to estimate food volumes comparing with weighed food intake measured from plate waste method.

## 2. STUDY POPULATION

### Study Design

To validate the accuracy of DietCam in analyzing food images taken by Sony Smarteyeglass in food recognition and volume estimation, a 2x2x2x2x3 mixed factorial design will be used, with a between-subject factor of the order of meals (Order 1 and 2) and within-subject factors of food shapes (Regular and Irregular), food complexities (Single food and Mixed food), meals (Meal A and B), and methods of measurement (DietCam, weighed food intake [WFI], and 24-hour dietary recall) (see Table 1). Individuals will be randomized into one of the two orders of meals. In each meal, participants will be given a meal that includes a regular-shaped single food (i.e., cookie), an irregular-shape single food (i.e., ice cream), a regular-shaped mixed food (i.e., sandwich), and irregular-shaped mixed food (i.e., pasta dish). Dependent variables will be the identification of foods and amount of foods consumed.

**Table 1. Description of Study Design**

Order	Meal Session 1	Meal Session 2
1 (n=15)	
Meal A:
 
Turkey & Provolone Cheese Sandwich (Regular-shaped mixed food)
 
Chicken and Wild Rice (Irregular-shaped mixed food)
 
Chocolate Chips Cookie (Regular-shaped single food)
 
Potato Chips Original (Irregular-shaped single food)
	
Meal B:
 
Ham and Cheddar Cheese Wrap (Regular-shaped mixed food)
 
Pasta with Broccoli in Alfredo Sauce (Irregular-shaped mixed food)
 
Red Seedless Grapes (Regular-shaped single food)
 
Chocolate Ice-cream (Irregular-shaped single food)

2 (n=15)	
Meal B:
 
Ham and Cheddar Cheese Wrap (Regular-shaped mixed food)
 
Pasta with Broccoli in Alfredo Sauce (Irregular-shaped mixed food)
 
Red Seedless Grapes (Regular-shaped single food)
 
Chocolate Ice-cream (Irregular-shaped single food)
	
Meal A:
 
Turkey & Provolone Cheese Sandwich (Regular-shaped mixed food)
 
Chicken and Wild Rice (Irregular-shaped mixed food)
 
Chocolate Chips Cookie (Regular-shaped single food)
 
Potato Chips Original (Irregular-shaped single food)

### Participants

Thirty men and women will be invited to participate in the validation study. Eligibility of this investigation will be based upon the following criteria: 1) between the ages of 18 and 65 years; 2) body mass index (BMI) 18.5 to 24.9 kg/m^2; 3) no food allergies/intolerance to foods used in the investigation; 4) report not having a dietary plan or dietary restrictions that prevents consumption of the foods used in the investigation; 5) report a favorable preference for the foods served in the meal (listed in Table 2), with participants rate each food item  3 on a Likert

scale during the phone screen; 6) able to complete all two meal sessions within four weeks of the screening session; 7) are not legally blind without corrected lenses; and 8) are able to eat a meal while wearing the Sony Smarteyeglass. Participants will be excluded if they wear electronic medical devices such as pacemakers and implantable defibrillators.

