## Recruitment

Participants will be recruited from the University of Tennessee, Knoxville campus by posting flyers around campus and handing out flyers around campus and sending emails through University electronic mailing lists. Participants will be asked to contact the Healthy Eating and Activity Laboratory (HEAL) by phone and will be given information about a study that investigates dietary assessment via digital images. Interested participants will be screened over the phone and scheduled for a face-to-face screening session. Participants who sign the consent form at the screening session and meet eligibility criteria will be randomized to one of two orders.

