## 3. STUDY PROCEDURES

### Procedures

All participants will be asked to come to HEAL for 1, 30-minute screening session, and then for 2, 40-minute meal sessions, with approximately one week occurring between each session. Sessions will be scheduled between 11:00am and 5:00pm, Monday to Friday. During the screening session, interested participants will sign the consent form. After signing the consent form, eligibility will be confirmed by taking height and weight measures. Participants will also be given questionnaires related to demographics. Prior to the start of the first meal session, eligible participants will be randomized to one of the two orders described in Table 1, using a random numbers table. Participants will be instructed for the meal sessions to stop eating a minimum of two hours prior to the scheduled meal sessions and only consume water during that period.

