**During both meal sessions, instructions on how to use Sony Smarteyeglass will be provided to participants. These instructions will include how to wear and use the eyeglasses. Participants will be instructed that, after putting on the Smarteyeglass, to initiate the recording via the controller of the Sony Smarteyeglass. After the recording is initiated and prior to starting to eat, participants will be instructed to look at each provided food at the table. Then, participants will also be instructed to turn their head toward the left shoulder, look at each food from the side, and then repeat the same step for turning their head toward the right shoulder. Participants will be asked to start the meal by taking one bite of each provided food. For the first bite of each food, participants will be instructed to hold the food, either in their hand or on a fork or spoon (depending on the food), approximately 12 inches in front of the eyeglasses and to look at the food. Following taking the first bite of each provided food, participants will be instructed to eat normally until satisfied. Participants will be given 30 minutes to eat. The investigator will leave the room while the participant is eating. The investigator will check in with participants every 10 minutes. At the end of 30 minutes, participants will be instructed to again look at each provided food on the table at three different angles (looking straight at each food, from left side and the right side) following the exact same procedure at the beginning of the meal. The second meal session will follow the same procedure as the first session.**

On the day following each meal session, participants will be called to complete a 24-hour dietary recall, which will take 20 minutes to complete. Instructions will be provided to participants at the end of each meal session about how to complete the dietary recall and a two-dimensional visual aid will be provided to aid participants in estimating the consumed portions for each food and beverage item consumed.

At the end of second meal session, participants will be asked to complete a questionnaire to provide feedback on their use of the Sony Smarteyeglass. After the second session is completed, the participants will be thanked for their participation and given a \$20 gift card to compensate for their time in the study.

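### No check of criterion 8 is described before randomisation, and device feedback is taken only at the end of session 2, so the usability percentages cover completers only and may be too favourable

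*Protocol*

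**What the plan says.** - **Entry condition.** Criterion 8 in the Protocol, Participants, requires that people "are able to eat a meal while wearing the Sony Smarteyeglass". Recruitment says that those who consent and meet the criteria go on to be randomised, so criterion 8 has to be settled by then.
- **Steps before randomisation.** Recruitment: "Interested participants will be screened over the phone and scheduled for a face-to-face screening session". The phone-screen content that the protocol names is food ratings (Participants) and self-reported height and weight (Measures). For the visit itself, Procedures says: "After signing the consent form, eligibility will be confirmed by taking height and weight measures".
- **Randomisation.** "Prior to the start of the first meal session, eligible participants will be randomized" (Procedures).
- **First described use of the device.** "During both meal sessions, instructions on how to use Sony Smarteyeglass will be provided to participants" (Procedures). No earlier wear is mentioned.
- **Feedback.** "At the end of second meal session, participants will be asked to complete a questionnaire" (Procedures). Measures, under Participants' Feedback, places it after the last meal session. It covers ease of use, clarity of instructions, satisfaction, likelihood and comfort on a five-level rating, and reports percentages of those answering.
- **Role of the feedback.** The two specific aims are accuracy in recognising foods and accuracy in estimating volume. The dependent variables under Study Design match them.

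**The concern.** Criterion 8 is worded as an ability, whereas criteria 4 and 5 are worded as self-report. Someone who has never worn the device can only guess whether they can eat a meal in it. As described, the first real test comes at session 1, after the order has been allocated. A person who finds then that they cannot manage has been randomised while failing an entry criterion, and the text shown does not say what happens next.

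If that person stops, they are also lost to the questionnaire. Ease of use, satisfaction and comfort are the items on which someone who gave up would be expected to score the device worst, and they are the ones not asked. Measures provides for counting blurred images and capture failures, but not participants who could not tolerate the device, so the selection would not show in the report either. An analysis plan can define a denominator, but it cannot recover answers that were never collected.

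**Working it through.** **Sequence.** Phone screen; 30-minute screening visit (consent, height and weight, demographics); randomisation; session 1 (first described wear); session 2; questionnaire. Two things follow from the text alone:

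1. No step before randomisation is described as testing criterion 8.
2. Anyone who leaves between randomisation and the end of session 2 gives no feedback.

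**Inputs.** N = 30, as 15 per order (Table 1; 15 + 15 = 30 agrees with Participants). The protocol gives no dropout rate, intolerance rate or expected rating, so there is no figure of its own to reproduce. Everything below is an assumed range.

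**Effect on a favourable percentage.** Let k people stop before the end of session 2, and let f of the 30 − k completers answer favourably. In the worst case all k would have answered unfavourably:

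overstatement = f/(30 − k) − f/30 = [f/(30 − k)] × k/30

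| k | Observed | Of all 30 | Overstatement (points) | Range for observed shares of about 60% to 100% |
|---|---|---|---|---|
| 0 | – | – | 0 | 0 |
| 1 | 23/29 = 79.3% | 23/30 = 76.7% | 2.6 | 2.0 to 3.3 |
| 3 | 22/27 = 81.5% | 22/30 = 73.3% | 8.1 | 5.9 to 10.0 |
| 5 | 20/25 = 80.0% | 20/30 = 66.7% | 13.3 | 10.0 to 16.7 |

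The worst case is one end of a range. If three people stopped for unrelated reasons and all would have been favourable, the full figure would be (22 + 3)/30 = 83.3%, slightly above the observed 81.5%. The direction is therefore likely rather than certain.

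**Chance of any loss.** With an assumed stopping rate d, the expected loss is 30d and the chance of at least one loss is 1 − (1 − d)^30:

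| d | Expected loss | Chance of at least one |
|---|---|---|
| 2% | 0.6 | 46% |
| 5% | 1.5 | 79% |
| 10% | 3 | 96% |
| 20% | 6 | over 99% |

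**What each remedy does.** Take k = 3 again.

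- If the three are screened out by a try-on, the table still shows 22/27 = 81.5%, because they never reach the questionnaire.
- If they are randomised and asked when they stop, the denominator returns to 30 and the figure becomes 73.3% under the same assumption.

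Only the change in questionnaire timing moves the percentages.

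**The case against.** The case on the other side is substantial, and several stronger readings fall to it.

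- **A reader might infer that criterion 8 cannot be checked until after randomisation.** The protocol does not support that. A phone screen and an in-person visit both come first, and only eligible people are randomised. Naming height and weight does not say that nothing else is checked: no specific check is described for several other criteria either, the text is a synopsis, and the phone script is not shown. What stands is that no check is described.
- **A reader might infer that wearers of prescription glasses will fail, or that people who struggle will be removed.** Nothing says that the device cannot be worn with correction, and no rule removes a participant who struggles. Someone who dislikes the device but finishes both meals does give feedback.
- **A reader might infer damage to the order balance or to the accuracy results.** The comparison of methods is within subject, and no link between meal order and intolerance is stated. A 15/12 split needs all three of three losses in one order. If losses fall at random, that has probability 2 × C(15,3)/C(30,3) = 910/4060 = 22%, so it is an unfavourable case and not the expected one.
- **Criterion 8 already limits the population to people able to eat in the device.** For that population, ratings from able users are not biased; they only fail to generalise beyond it. This stands in part. It does not cover a randomised person who used the device once and stopped, whose view belongs in a report on its use.
- **In Measures, the last meal session could be read as the last one attended.** Procedures fixes it as the second, so the two agree only for completers.

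**Conclusion.** The point holds in a limited form. The protocol describes no check of criterion 8 before randomisation, and its questionnaire timing restricts the usability percentages to people who finish both sessions. Those percentages may be too favourable.

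The size cannot be derived from the protocol. It is zero without dropout. If every person who stops would have been unfavourable, it is about 2 to 3 points for one loss, 6 to 10 for three and 10 to 17 for five. Those loss counts and that assumption about ratings are illustrations, not protocol figures.

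The feedback is a descriptive tabulation outside the two aims, and the accuracy comparisons are not directly affected. Severity is minor: the point is worth acting on because the change is nearly free.

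**What to change.** 1. **Questionnaire timing (Procedures, and Participants' Feedback under Measures).** Give the questionnaire at the end of the last meal session attended, including when a participant stops early. Tabulate it over all randomised participants who used the device, and state how many stopped early and how many did not answer. People who stop at session 1 will be rating one use rather than two, so show them separately as well as in the total.
2. **Criterion 8 (Participants and Procedures).** State how and when it is judged. A brief try-on with usual vision correction fits the screening visit that already exists ("1, 30-minute screening session, and then for 2, 40-minute meal sessions") and comes before randomisation. Report the number who fail. A short wear without food is only a partial test of eating a meal in the device. It limits losses after randomisation but does not correct the feedback percentages.

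The cost is a few minutes at screening with the study's own device and a changed phrase in two places. The try-on may produce a few more screen failures, and the timing change may make the feedback figures slightly less favourable.

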## Recruitment

Participants will be recruited from the University of Tennessee, Knoxville campus by posting flyers around campus and handing out flyers around campus and sending emails through University electronic mailing lists. Participants will be asked to contact the Healthy Eating and Activity Laboratory (HEAL) by phone and will be given information about a study that investigates dietary assessment via digital images. Interested participants will be screened over the phone and scheduled for a face-to-face screening session. Participants who sign the consent form at the screening session and meet eligibility criteria will be randomized to one of two orders.

## 3. STUDY PROCEDURES

### Procedures

All participants will be asked to come to HEAL for 1, 30-minute screening session, and then for 2, 40-minute meal sessions, with approximately one week occurring between each session. Sessions will be scheduled between 11:00am and 5:00pm, Monday to Friday. During the screening session, interested participants will sign the consent form. After signing the consent form, eligibility will be confirmed by taking height and weight measures. Participants will also be given questionnaires related to demographics. Prior to the start of the first meal session, eligible participants will be randomized to one of the two orders described in Table 1, using a random numbers table. Participants will be instructed for the meal sessions to stop eating a minimum of two hours prior to the scheduled meal sessions and only consume water during that period.

**During both meal sessions, instructions on how to use Sony Smarteyeglass will be provided to participants. These instructions will include how to wear and use the eyeglasses. Participants will be instructed that, after putting on the Smarteyeglass, to initiate the recording via the controller of the Sony Smarteyeglass. After the recording is initiated and prior to starting to eat, participants will be instructed to look at each provided food at the table. Then, participants will also be instructed to turn their head toward the left shoulder, look at each food from the side, and then repeat the same step for turning their head toward the right shoulder. Participants will be asked to start the meal by taking one bite of each provided food. For the first bite of each food, participants will be instructed to hold the food, either in their hand or on a fork or spoon (depending on the food), approximately 12 inches in front of the eyeglasses and to look at the food. Following taking the first bite of each provided food, participants will be instructed to eat normally until satisfied. Participants will be given 30 minutes to eat. The investigator will leave the room while the participant is eating. The investigator will check in with participants every 10 minutes. At the end of 30 minutes, participants will be instructed to again look at each provided food on the table at three different angles (looking straight at each food, from left side and the right side) following the exact same procedure at the beginning of the meal. The second meal session will follow the same procedure as the first session.**

On the day following each meal session, participants will be called to complete a 24-hour dietary recall, which will take 20 minutes to complete. Instructions will be provided to participants at the end of each meal session about how to complete the dietary recall and a two-dimensional visual aid will be provided to aid participants in estimating the consumed portions for each food and beverage item consumed.

At the end of second meal session, participants will be asked to complete a questionnaire to provide feedback on their use of the Sony Smarteyeglass. After the second session is completed, the participants will be thanked for their participation and given a \$20 gift card to compensate for their time in the study.

For the first and second meal session, the meals will contain foods that are categorized into two food shapes (Regular and Irregular) and two food complexities (Single food and Mixed food). Each meal will contain four foods (see Table 2 for detailed description of foods), with the four foods representing the four potential food categories (regular-shaped single food, irregular-shaped single food, regular-shaped mixed food, irregular-shaped mixed food). Along with the four foods, participants will be given 20oz of water in each meal session. Foods will be weighed prior to being provided to participants and the amount provided to participants will be within +/- 3g of the amount described in Table 3. Mixed foods will be broken down into their individual food components and measured. Each meal will provide approximately 50% of daily estimated energy need for each sex. The Estimated Calories Needed Per Day for males and females aged 19 to 35 years are 2450 kcal/day and 1900 kcal/day, respectively. Thus, each meal will provide approximately 1225 kcal for males and 950 kcal for females. Each food will provide approximately 25% of the energy for each meal.

